5.1 Power Estimation

Power estimates for each outcome assumed a 5% significance level. Totally, N=120 subjects will be randomized in 1:1:1 ratio to the three treatment arms, that is, 40 subjects to each arm. Using the same 16% drop-out rate experienced in our previous study and that 87% of the completers possess a valid driver's license, a national average published by the Department of Transportation, power was calculated for 33 subjects per treatment arm (total N=99) for Aims 1 and 2, and 29 subjects per treatment arm (total N=87) for Aim 3. We have 80% power to detect effect sizes equivalent to Cohen's $d=0.54$ and $d=0.58$ for sample sizes 33 and 29 respectively. This effect size is based on differences between groups of changes from baseline at the end of the study (week 8). The power is calculated using specific formulas for a time-by-treatment interaction in a longitudinal linear mixed-effects model {Diggle PJ, Heagerty P, Liang KY, Zeger SL: Analysis of Longitudinal Data, 2nd edition, 2002, Oxford University Press, Oxford, p.29}. Power is expected to be higher for larger effect sizes and fewer dropouts.

6. Data and Safety Monitoring Committee (DSMC)

Progress reports will be presented to the DSMC every 6 months. Two reports (open and closed reports) will be generated and presented in two sessions.

Key study personnel and all DSMC members will attend the open session; *the open report* will present data in aggregate form (not by arm). Open session attendees will review presented summarized data for data completeness and accuracy (e.g., review ranges for numeric variables to catch any outliers/unusual observations).

The closed session will include only the study statistician and members of the DSMC; *the closed report* will present data by treatment arm, but in blinded fashion,

i.e., arms will be presented as arm X, arm Y, arm Z. Treatment labels can be revealed to the DSMC members upon their request if major concerns arise. Statistical comparison of relevant characteristics between the arms will be done. No interim analysis comparing primary outcomes between the arms will be performed in order to preserve the power of the primary analysis and the overall Type I error at 0.05 level till the end of the study, unless requested by the DSMC. Members of the DSMC will be asked to maintain confidentiality related to the interim data presented in the closed report until the end of the trial.

Number of available observations (N) will be given for each variable to give a sense of data collection completeness. The reasons of data entry lagging, leading to a large portion of missing values, will be provided.

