If already using cannabis, participants will be asked to slowly taper cannabis use over a one-week period (Baseline Week - Figure 1) so that they are only using study medications during the remaining 10 weeks of the clinical trial. If unable to abide by this, subjects will not be allowed to participate in the study. Participants will be asked to abstain from cannabis 7 days prior to study entry. In order to ensure abstinence, we will use the Draeger 5000 saliva screening test for tetrahydrocannabinol at their first experimental visit to ensure that they have adhered to this period of abstinence before the study. A level above 5 ng/ml will indicate recent use and the appointment will be rescheduled.

Baseline Period:

If eligibility criteria (see below) are met, subjects will be instructed on completing a paper diary (Appendix 4). Provided their VAS pain intensity remains above 3/10 during the Baseline Week, they will be given oral and herbal study medication (and a Volcano Vaporizer) at the next study visit one week later.

At the baseline visit, participants will be given the Beck Depression Inventory (BDI-II) in order to screen for depression and suicidality. They will also be given the AUDIT and DAST to screen for substance use problems. The PSQ and Mood Disorder Questionnaire will also be administered to screen for Schizophrenia and Bipolar Type I, respectively. The painDETECT Questionnaire will be administered to distinguish neuropathic low back pain from non-neuropathic low back pain. The Survey of Cannabis Use will be administered during this period to obtain information on the cannabis use habits of the participant.

Should the participant choose to participate in the driving simulation portion of the study, the Driving History and Habits Questionnaire will be administered to obtain information on participant driving history, should they decide to participate in the driving simulation study portion.

Telephone Interview:

To determine eligibility, each prospective participant will be asked the following questions from the NIH Chronic Low Back Pain Definition:

1. Do you have low back pain?

No	STOP.....	0
Yes		1

2. How long has low back pain been an ongoing problem for you?

Less than 1 month	0
1-3 months	1
3-6 months	2
6 months -1 year	3
1-5 years	4
More than 5 years	5

3. How often has low back pain been an ongoing problem for you over the past 6 months?

[figure not shown]
Every day or nearly every day in the past 6 months	0

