Subjects will be instructed on the use of a vaporizer at the visit prior to Week 1. The manufacturer's instructional brochure (Appendix 6) will be reviewed. In order to ensure consistency of dosing throughout the study, they will also be instructed on the use of the Foltin puff procedure at the visit prior to Week 1 (Appendix 7). A copy of both of these documents will be provided for review at home.

On completion of eight weeks of treatment or at the time of withdrawal from the study, patients will completely taper their cannabis over a period of one to two weeks to avoid withdrawal symptoms. Cannabis withdrawal symptoms will be measured via a phone call after Taper weeks 1 and 2 (Appendix 8). Questions (Appendix 26) will be added to access subject's beliefs of what they received (e.g., THC or placebo) after the first week and again after the eighth week. This will enable us to assess the effectiveness of blinding and thus report on the assay sensitivity of the study. The optimal

timing and frequency of blinding assessments has not been established. Thus, we will use a strategy to collect blinding data two times from participants: shortly after randomization and at the end of the trial. This will permit a comparison of blinding at the two stages.

If a subject does not participate in the driving simulation or the microbiome substudy, we will test their oral fluid for the presence of THC using the Draeger 5000. This will be done to exclude participants who use their own cannabis seeking pain relief because they were given placebo.

An online questionnaire will be deployed (Appendix 27). Potential participants will complete this using HIPAA compliant software, the Platinum Edition of Survey Monkey. Please see <https://www.surveymonkey.com/pricing/details/> for verification of the HIPAA compliance of this survey.

Outcome Measures:

DAILY TESTING IN SUBJECT'S RESIDENCE USING PAPER DIARY

Medication intake: The timing and number of puffs of vaporized cannabis or placebo THC), oral medication (dronabinol or placebo), and breakthrough pain medication will be chronicled. (5 minutes)

REPEATED TESTING AT STUDY VISITS

Center for Medicinal Cannabis Research Forms

- Neurobehavioral Medical Screen: The clinician will fill this out to record any events that may have occurred between visits to confound results from the Neuropsychological testing such as an any trauma to the head or any open head wounds.

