Cannabis Withdrawal Scale: The Cannabis Withdrawal Scale can be used as a diagnostic instrument in clinical and research settings where monitoring of withdrawal symptoms is required.²² This will be performed after the 2-week tapering period has concluded. (10 minutes) If there was a previous adverse event or events (AE(s)), the Cannabis Solicited Adverse Events instrument will again be administered to ensure that the AE(s) have resolved. Participants will continue to be followed until there is resolution of the AE(s).

ARM #2. Driving Simulation:

Subjects with drivers’ licenses will be scheduled for two experimental visits; one before they begin the randomized controlled trial, and a second visit after finishing their 8th week treatment. The initial visit will involve a 20-minute session to garner baseline values for driving skills. This visit will coincide temporally with the first session for the randomized controlled trial prior to Week 1 (Appendix 12).

At the time of the second driving simulation visit, subjects will be assigned the same medication that they have been using during the randomized controlled trial. Using a Volcano Vaporizer, subjects will inhale the average number of puffs they had consumed per session throughout the four previous weeks of the randomized controlled trial. They will use the Vaporizer before Hour 2 and again before Hour 6 (Table 3). They will also take the same oral medication that was provided during the randomized controlled trial. In addition to examining the effects on driving simulation, acute effects of study medications on spontaneous pain and vital signs will be determined (Appendix 13). We will administer the simulator sickness assessment during the first 2 hours of the appointment to ensure that the participant is physically able to perform the driving simulation tasks.

At the beginning of driving simulation appointments, participants will be given a urine toxicology and a breathalyzer test to test for any illicit substances that is not prescribed by a physician. Should the participant screen positive for an illicit substance, they will either be asked to reschedule or be discontinued from the study at the Principal Investigator's discretion. If this happens, participants will be compensated \$10 for arriving to the scheduled appointment.

During the Driving Simulation study visit, the participants will be given paper and pencil forms that measure the following:

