By conducting repeat assessments for four hours following the first vaporization, we will be able to determine at what point participants no longer exhibit acute effects for each of the study medications. Participants will then complete a second vaporization and ingestion of oral medication before hour 6. We will then assess them for three hours in order to determine whether the acute effects are similar to those seen after the first vaporization, or perhaps greater (due to cumulative/residual effects). To minimize the novelty of the driving simulations, participants will complete a pretest training session to re-familiarize themselves with the hardware and the tasks that they are to encounter during the simulations. Four separate tasks will be embedded within the simulation.

Table 3 Assessments of Acute Effects One Day following 2 and 8 Weeks of Cannabis Treatment

Hour	1		2	3	4	5		6	7	8
		Vaporization/Oral Medication					Vaporization/Oral Medication			
Vital Signs	X		X	X	X	X		X	X	X
Numerical Pain Intensity Score	X		X	X	X	X		X	X	X
Cold Pressor Test	X		X					X		
Pain Relief			X	X	X	X		X	X	X
Psychoactive Effects			X	X	X	X		X	X	X
Driving Simulation	X		X	X		X		X	X	X
iPad Performance Testing	X		X	X		X		X	X	X
Blood Draw ($\Delta 9$ -THC levels)	X		X	X	X	X		X	X	X

Driving simulations: Simulation hardware will consist of a 3-screen, wide field-of-view monitor setup, steering wheel, and accelerator and brake pedals. The fully interactive simulations will assess lane tracking (standard deviation of lateral position [SDLP], or “weaving”), response to divided attention stimuli (accuracy, response time), car following, and performance during scenarios simulating routine driving as well as crash avoidance situations.

Participants in the simulator study will also be assessed for far visual acuity (Snellen Visual Acuity eye chart; need to have acuity of 20/40 or better, with or without correction), color vision, and contrast sensitivity (Vistech Contrast Sensitivity (Pelli-Robson Chart)). Participants will complete an orientation and practice drive prior to the initial simulation, in order to familiarize them with the controls and roadways.

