2.2 Study enrollment, Randomization, and dropout

The 120 eligible participants will be randomized to Arm A (vaporized Δ9-THC (3.5%)/placebo oral pill, n=40), to Arm B (dronabinol/vaporized placebo THC, n=40), or Arm C (double placebo, n=40). With a 16% dropout rate, we expect 33 subjects completing the 8-week visit for each arm. The completers who have a valid driver's license will implement driving simulation. The number (%) of subjects randomized, number (%) of subjects completing the 8-week-treatment, and number (%) of patients lost to follow-up will be summarized overall and by treatment arm. Fisher's exact test will be used to compare the arms in the proportions of lost to follow-up. Reasons (if known) for lost to follow-up will also be recorded. The comparisons are following an order of importance: arm A vs. arm B; arm A vs. arm C; arm B vs. arm C. Since the three comparisons have different levels of importance, no correction will be done for multiple comparisons.

The dropouts and completers will be compared, overall and stratified by treatment arm, with respect to their baseline demographics, medical characteristics, and the prevalence and timing of adverse events. The statistical analysis will use Fisher's exact test for binary and nominal variables, Student's t test or Wilcoxon rank-sum test for continuous variables, and log-rank test for time-to-event analysis, censored at the time of dropout.

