4.2.3 Comparison of subjective and psychoactive side effects between treatment arms

Psychoactive effects will be assessed at 1, 2, 3, 4, 5, and 6 hours after the first acute administration of treatment at the driving simulation visit in a substudy. Area under the time concentration curve (AUC) will be used as a measure for the aggregate effect of response over a period of time (during 1-6 hours after the 1st dose). AUC will be compared between the arms using linear regression (Aim 2).

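### SAP 5.1 does not describe the power of the driving-substudy outcomes: 33 per arm for an Aim 2 outcome expected in 29, full uptake of an optional session, and a six-visit formula for single-value comparisons

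*SAP*

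**What the plan says.** - **Power.** SAP 5.1 starts from 40 per arm and applies 16% dropout and an 87% licence rate among completers. It reports that "power was calculated for 33 subjects per treatment arm (total N=99) for Aims 1 and 2, and 29 subjects per treatment arm" for Aim 3, and gives 80% power at d=0.54 (n=33) and d=0.58 (n=29). It bases d on change from baseline at week 8 and cites a longitudinal time-by-treatment formula.
- **Psychoactive outcome.** SAP 4.2 and 4.2.3 place the psychoactive ratings at the driving visit of a substudy of licensed completers. They are reduced to one AUC per person: "AUC will be compared between the arms using linear regression (Aim 2"). Protocol section 9 (Arm #2) likewise gives the 15 VAS ratings at driving simulation.
- **Driving outcome.** SAP 4.2.4 compares SDLP and coherence after 8 weeks of treatment by ANOVA. A separate repeated-measures model then covers the acute effects.
- **Who takes part.** SAP 2.2 says that completers with a valid licence do so without condition ("license will implement driving simulation"). Protocol section 9 treats driving as a choice: "Should the participant choose to participate in the driving simulation portion of the study" under Baseline Period, and "If a subject does not participate in the driving simulation or the microbiome substudy" in the text after Table 1, where a separate oral-fluid test is planned for such people. SAP section 1 is also conditional.
- **Screens.** Protocol section 9 (Arm #2) requires vision ("need to have acuity of 20/40 or better, with or without correction"), a urine and breath test after which those positive for an illicit substance may be lost ("they will either be asked to reschedule or be discontinued from the study"), and a simulator-sickness check in the first 2 hours.

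**The concern.** Three features of the power statement do not match the substudy. One Aim 2 outcome is credited with people who are not expected to supply it. The count of 29 allows for no refusals and no failed screens. And the effect sizes come from a design with six measurements over 8 weeks, whereas two of the planned substudy comparisons use one value per person.

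Aim 3 is one of the trial's three aims and concerns driving safety. SAP 4.2.4 sets no equivalence margin, so the stated detectable effect is the reader's main guide to what a non-significant driving or psychoactive result can exclude. If that effect is too small, such a result will look more informative than it is.

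**Working it through.** **Inputs.** From SAP 5.1: 40 per arm, 16% dropout, 87% licensed, 5% significance, 80% power. From SAP 4.1.1: baseline and weeks 1, 3, 5, 7, 8. The SAP does not state sidedness; two-sided testing reproduces its figures, so z = 1.96 + 0.84 = 2.80.

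**1. The counts reproduce.** 40 × 0.84 = 33.6, taken as 33. Then 33 × 0.87 = 28.7 (or 33.6 × 0.87 = 29.2), giving 29. The licence rate is the only step from 33 to 29.

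**2. The effect sizes reproduce from the slope formula.** With m per arm, slope difference b, outcome SD s and within-person correlation ρ:

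m = 2(2.80)² s²(1−ρ) / (SSx b²)

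The visit times average 24/6 = 4, so SSx = 16+9+1+1+9+16 = 52. The week-8 difference is 8b and the SD of change is s√(2(1−ρ)). In units of that SD, ρ cancels:

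d = 8 × 2.80 / √(52m)

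- m=33: 22.41/41.42 = 0.541 (stated 0.54)
- m=29: 22.41/38.83 = 0.577 (stated 0.58)

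The other formulas tried do not match. At n=33 and n=29 they give 0.690 and 0.736 (two-sample normal), 0.700 and 0.749 (t-test), 0.612 and 0.653 (one-sided normal), and 0.480 and 0.512 (one-sided slope).

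**3. Fit to the substudy analyses.** The AUC is one number per person, and Protocol Table 3 shows no psychoactive rating at Hour 1, before dosing. The ANOVA after 8 weeks uses post-treatment values at one stage. Neither is a slope over six visits. For an unadjusted pairwise comparison of single values at 29 per arm:

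- Detectable d = 2.80 × √(2/29) = 0.736 by the normal formula, and 0.749 by the t-test with 56 degrees of freedom.
- The noncentrality is d × √(29/2) = 3.81d. This is 2.06 at d=0.54 and 2.21 at d=0.58. Power by the t-test is about 52% and 58%, against the 80% stated.

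**4. Uptake.** The documents give no participation or screen-pass rate, so the rates below 100% are assumptions. Counts are 29.2 × rate, rounded down. Detectable d is for a two-sample t-test at 80% power.

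| Licensed completers assessed | n per arm | Detectable d |
|---|---|---|
| 100% (SAP) | 29 | 0.75 |
| 90% | 26 | 0.79 |
| 80% | 23 | 0.84 |
| 70% | 20 | 0.91 |
| 60% | 17 | 0.99 |

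**The case against.** The strongest defence is that SAP 5.1 contains no arithmetic error and already prints the n=29 figure, so moving one secondary outcome from d=0.54 to d=0.58 is minor. The arithmetic is indeed sound. But the n=29 figure rests on the same six-visit formula, so relabelling the AUC would not by itself give the right detectable effect.

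Several stronger readings are tempting and go too far:

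- *All of Aim 2 loses its 33 per arm.* It does not. POMS, BDI-II, HVLT, Digit Symbol, pegboard and the M-scale, itself a psychomimetic measure, are collected at study visits.
- *29 is a ceiling.* It is an expected count. A higher licence share or lower dropout would raise it, and so might the replacement of people who cannot tolerate the minimum dose, depending on what the 16% includes.
- *The screens will remove many people.* The documents give no loss rate. A positive toxicology result may lead to rescheduling, toxicology is also screened at entry, acuity may be corrected, and the sickness check falls within the visit. Protocol section 9 also says that licensed subjects will be scheduled for both driving visits.
- *Power for the AUC falls only to about 75%.* This comes from rescaling the SAP's d=0.54 from 33 to 29 per arm. It keeps the six-visit formula, which does not apply to a single AUC.

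It also stands that the two-sample figures are unadjusted. Adjustment for baseline driving could lower the detectable d, and pooling the variance over three arms would move it slightly towards 0.74. The acute repeated-measures driving model is not covered by this calculation.

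**Conclusion.** The point holds in limited form. The SAP contradicts itself on the sample size for the psychoactive AUC, and this needs no outside assumption. SAP 2.2 conflicts with Protocol section 9 and SAP section 1 on whether driving is optional, and 29 per arm leaves no room for refusal or a failed screen. The stated effect sizes do not describe the AUC regression or the driving ANOVA after 8 weeks.

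At the SAP's own 29 per arm, the detectable d is about 0.75 rather than 0.54 or 0.58. This rests on two-sided 5% testing and unadjusted pairwise comparisons. Anything beyond 0.75 depends on an uptake rate that the documents do not give.

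These are secondary substudy outcomes. The primary pain comparison does not depend on the driving substudy. The correction should be made, but it does not threaten the trial's main result.

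**What to change.** 1. In SAP 5.1, assign the psychoactive AUC to the substudy sample size and keep 33 per arm for the Aim 2 visit measures.
2. Restate the detectable d for the AUC and the driving comparison after 8 weeks, using a formula that matches each analysis. Give it at 29 per arm and over a stated range of uptake and screen passing, such as 60–90%. If the analysis will adjust for baseline driving, state the correlation assumed. State separately what the acute repeated-measures model can detect.
3. Reconcile SAP 2.2 with Protocol section 9 and SAP section 1, for example by limiting the substudy to licensed completers who agree and pass the driving checks.

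The cost is SAP wording and a short table. No extra enrolment or change of analysis is needed. The stated figures for these outcomes will look less favourable.

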4.1.1 Primary analysis

The primary analysis will be the comparison of self-reported pain intensity between arm A and arm B. An intent-to-treat analysis will be performed on data from participants who complete baseline. Data transformation (e.g., log10, square root) may be performed to improve distribution normality as appropriate. Response profiles analysis will be performed if the trend of pain intensity over time is not linear. We will compare different covariance pattern models (e.g., unstructured, compound symmetry) based on AIC and identify a covariance model with the best fit to our data. This is a randomized controlled trial so that we can remove main group effect with assumptions about equal mean responses (i.e., pain scores) at baseline for the three treatment arms. Weekly or biweekly average of pain intensity from the daily diary will be calculated as a primary outcome. Time will be treated as a factor with 6 levels (i.e., baseline, weeks 1, 3, 5, 7, 8), and the mean response profiles will be compared between the arms. The treatment effect over time will be assessed by the significance of the treatment arm x time interaction using Wald test. Also, average change at the treatment period (weeks 5-8) from baseline will be compared between the groups. (Aim 1)

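### The 80% power figures in SAP 5.1 are not tied to a stated test: d=0.58 does not describe either planned driving analysis, and d=0.54 does not assure 80% for the 5-df pain test in SAP 4.1.1

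*SAP*

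**What the plan says.** **Power (SAP 5.1).** "We have 80% power to detect effect sizes equivalent to Cohen's $d=0.54$ and $d=0.58$ for sample sizes 33 and 29 respectively". The scale is given as follows: "This effect size is based on differences between groups of changes from baseline at the end of the study (week 8"). The method is a single one for all aims: "The power is calculated using specific formulas for a time-by-treatment interaction in a longitudinal linear mixed-effects model". On the error rate: "Power estimates for each outcome assumed a 5% significance level". The 33 per arm applies to Aims 1 and 2, and the 29 per arm to Aim 3.

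**Pain (SAP 4.1.1).** The A versus B comparison is primary. "Response profiles analysis will be performed if the trend of pain intensity over time is not linear". "Time will be treated as a factor with 6 levels (i.e., baseline, weeks 1, 3, 5, 7, 8"), and "The treatment effect over time will be assessed by the significance of the treatment arm x time interaction using Wald test". The section then adds: "Also, average change at the treatment period (weeks 5-8) from baseline will be compared between the groups". SAP 4.1 ranks the three arm pairs. Nothing ranks these two tests within the A versus B pair.

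**Driving.** SAP section 1 and Protocol section 9 (Arm #2) schedule two driving visits: a 20-minute baseline drive before treatment and a full day after week 8. Protocol section 20 pays for one session besides baseline. SAP 4.2.4 compares the 8-week driving measures between arms by ANOVA, then tests acute effects with a covariance pattern model over the day. Aim #3 (Protocol section 6) is about acute effects.

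**The concern.** An effect size at 80% power means something only with a named test, an SD unit and, for repeated measures, a correlation. SAP 5.1 gives none of these. If the figures come from a slope over six pain visits, they cannot be carried over to an endpoint measured at two visits and analysed by a week-8 ANOVA. They also do not carry over to the 5-df interaction test that SAP 4.1.1 writes out. At stake is whether the trial has the stated power for its primary comparison and for Aim 3, and whether the reader can tell which A versus B result decides the primary analysis.

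**Working it through.** **Inputs.** From SAP 5.1: 40 per arm, 16% dropout (40 × 0.84 = 33.6, used as 33), 87% licensed (33 × 0.87 = 28.7, used as 29), 5% significance (taken as two-sided) and 80% power, so z = 1.960 + 0.8416 = 2.8016. Pain time points are weeks 0, 1, 3, 5, 7, 8 (SAP 4.1.1). Correlations are assumptions, shown as ranges.

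**1. Reproducing the plan's figures.** For a slope test with compound symmetry and x = week/8, the week-8 difference detectable satisfies difference² = 2z²σ²(1−ρ)/(n·Sxx). Dividing by the SD of change, σ√(2(1−ρ)), gives d = z/√(n·Sxx), and ρ drops out. With x = 0, 0.125, 0.375, 0.625, 0.875, 1, Sxx = 0.8125.
- n=33: 2.8016/√26.81 = 0.541.
- n=29: 2.8016/√23.56 = 0.577.

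Both round to the stated values. This is really one match: any method scaling as 1/√n that gives 0.54 at 33 gives 0.54 × √(33/29) = 0.576 at 29. Two other routes also fit, with d in outcome SDs:
- two-point change, d = z√(2/n)·√(2(1−r)): 0.543 and 0.579 at r=0.69;
- baseline-adjusted comparison, d = z√(2/n)·√(1−r²): 0.541 and 0.577 at r=0.62.

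**2. Driving, week-8 ANOVA, n=29.** Pairwise contrast, pooled error from three arms (84 df), noncentrality d√(29/2).
- d in outcome SDs: 0.58 × 3.808 = 2.21, power 59%; 80% needs d=0.74.
- d in change SDs: multiply by √(2(1−r)). Power is 83%, 79%, 59% and 39% at r = 0.1, 0.2, 0.5 and 0.7, and crosses 80% at r of about 0.18.

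Protocol section 9 describes the lane-tracking measure as having good test-retest reliability, which fits poorly with r below 0.18.

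**3. Driving, two-visit change (not planned in SAP 4.2.4).**
- Change SDs: Sxx = 0.5, d = 2.8016/√14.5 = 0.736; power at 0.58 is about 60%.
- Outcome SDs: d = 0.87, 0.74, 0.57 and 0.47 at r = 0.3, 0.5, 0.7 and 0.8.

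The heading of Protocol Table 3 mentions 2 and 8 weeks. With a third visit at week 2, Sxx = 0.5417 and d = 0.71 in change SDs.

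**4. Driving, week-8 comparison adjusted for the baseline drive, n=29.** Divide an outcome-SD d by √(1−r²), 83 df. Required d for 80% at r = 0.3, 0.5 and 0.7: 0.71, 0.64 and 0.53 in outcome SDs; 0.60, 0.64 and 0.69 in change SDs.

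**5. Pain, A versus B, d=0.54, n=33.** Equal baseline means as in SAP 4.1.1, compound symmetry, d in change SDs. Noncentral chi-square with λ = (n/2)·δ′S⁻¹δ, where S is the covariance of the five post-baseline levels given baseline. The weeks 5-8 contrast averages levels 5, 7 and 8. Power at ρ = 0.3 / 0.5 / 0.8:

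| Effect shape | 5-df Wald | Weeks 5-8 contrast |
|---|---|---|
| Linear to week 8 | 76 / 67 / 59% | 90 / 81 / 68% |
| Ramp to week 4, then plateau | 90 / 80 / 69% | 97 / 93 / 83% |
| Week 8 only | 59 / 58 / 57% | 26 / 21 / 16% |
| Full at weeks 1 and 3, half at week 5, then none | 85 / 81 / 77% | 10 / 9 / 8% |

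For the last shape, d is the peak difference. In outcome SDs the 5-df test has 59 / 67 / 96% (linear) and 76 / 80 / 99% (plateau). With serial correlation (weekly 0.8 / 0.9 / 0.95, change SDs) it has 60 / 49 / 42% and 79 / 67 / 62%. Partial data from the 7 expected dropouts per arm add about 1 to 4 points in change SDs. A 1-df slope test with the baseline constraint has 93 / 88 / 83% (linear) and 97 / 92 / 84% (plateau).

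**6. Two tests.** Simulated under the null, the chance that at least one of the 5-df test and the weeks 5-8 contrast is significant at 5% is about 8.6%.

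**The case against.** The plan can be defended on several points.

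- **No arithmetic error is shown.** The figures reproduce. A reader might infer that a six-point formula was wrongly applied to driving, but its use is only inferred. With a two-point change in outcome SDs and r near 0.69, 0.58 is exactly right for two visits. This stands, and it also means that 0.74 cannot be given as the one correct figure for driving: it depends on the SD unit, and SAP 4.2.4 plans no two-visit change test. What it does not rescue is the planned ANOVA, which ignores the baseline drive.
- **The slope test may be intended for pain.** SAP 4.1.1 uses response profiles only if the trend is not linear, and a 1-df slope has 80% or more in the compound-symmetry cases tried. This is fair, but the slope test is never written out. Titration up to week 4 followed by a held amount (SAP section 1) makes a linear trend doubtful.
- **The weeks 5-8 comparison reads as subordinate.** It follows the interaction test and opens with an adverb of addition. That is a reasonable reading, though unstated. A reader might infer a type I error of 8.6%; this would need a rule that either test counts as success, and no such rule is written.
- **The within-day model may be adequately powered.** The slope formula on the seven driving hours of Protocol Table 3 (Sxx = 0.851) gives d=0.56, or 82% power at 0.58. That assumes a linear within-day effect and d in SDs of within-day change, whereas the day has two doses and SAP 4.2.4 plans a test of recovery. SAP 5.1 defines d by change to week 8, so it does not claim this.

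**Conclusion.** The concern holds as a mismatch between the power statement and the planned tests, with medium confidence. It should be fixed.

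**Driving** is the firmer part. A six-point figure describes neither analysis in SAP 4.2.4. For the week-8 ANOVA, d=0.58 at 29 per arm gives about 59% pairwise power in outcome SDs, and in change SDs it gives 80% only with a baseline to week-8 correlation that would be surprisingly low. The acute-effect model, which is the one that addresses Aim 3 directly, has no power figure of its own.

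**Pain:** 80% is not assured if the 5-df test is used. Power in change SDs under compound symmetry runs from 76% down to 59% for a linear effect and from 90% down to 69% for ramp then plateau, so some cases exceed 80%. A reader might infer that the primary analysis is underpowered; the documents do not support that, because the effect shape, correlation and SD unit are unstated.

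Nor do the numbers show that the weeks 5-8 contrast ought to decide. It gains for linear and plateau effects and loses badly for late-only or early-fading ones (8% to 26% against 57% to 85%).

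**What to change.** - **SAP 4.2.4:** adjust the week-8 driving comparison for the baseline drive already collected.
- **SAP 5.1, Aim 3:** replace d=0.58 with a figure for that adjusted test, stating its SD unit and assumed correlation (in outcome SDs about 0.71, 0.64 and 0.53 at r = 0.3, 0.5 and 0.7). State that it does not cover the within-day model.
- **SAP 4.1.1:** name in advance the one A versus B test that is decisive and label the other supportive. The weeks 5-8 contrast, the 5-df test and a written-out slope test are all possible. The choice is the sponsor's and should follow the effect shape expected.
- **SAP 5.1, pain:** restate power for the chosen test with its time points, degrees of freedom, correlation, effect shape and SD unit.

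The cost is SAP wording and a recalculated power paragraph, with no added patients or visits. The Aim 3 figure may look less favourable. Whichever pain test is made decisive, some effect shapes will show only in the supportive one.
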